Study staff will then prepare the participant for the NPU task with the application of physiological sensors. Next participants receive a series of shocks of increasing intensity (7 mA maximum) to assess their subjective tolerance threshold as per standard procedures from our laboratory^{22,128}. Their subjective maximum tolerated shock from the screening visit is used during the NPU tasks at both Visit 1 and Visit 2 to minimize individual differences in subjective pain tolerance. Next participants complete the NPU task (see below). After the NPU task, participants will be randomly assigned to drug group (doxazosin vs. placebo; between-subjects) in a stratified blocked schedule by sex using urn randomization procedures^{129,130}. The randomization and double-blind will be implemented and maintained by the UW Pharmaceutical Research Center (see letter of support), which is located in the same building as the CRU. All participants are told that they will receive either doxazosin or placebo during the study, but neither the participants nor the research staff will be aware of the group they are randomized to receive. Participants who are off study and were consented under a previous protocol which promised unblinding will still be unblinded, via phone contact after their last visit.

Participants will take the first study medication dose at home that evening after Study Visit 1 (Treatment Day 1). Staff will call participants on Day 2 to confirm initial compliance and monitor any adverse events. Participants continue 8 weeks of treatment including an 18-day escalating dose schedule up to a therapeutic dose (8 mg) of doxazosin (or placebo; see Doxazosin Dosing Schedule below). Additionally, participants will attend four medical monitoring visits during the first month of treatment (see below).

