Participants will return after 4 and 8 weeks of treatment (Study Visit 2 & 3) to complete a timeline-follow-back (TLFB) procedure to assess drinking since the previous visit to index drinks per days to asses heavy drinking days for this 8 week treatment period. At 4 weeks (Study Visit 2) we will again assess stress-reactivity in the NPU task. If participant reports a binge-drinking episode one week or less prior to Study Visit 2, staff will administer the CIWA-Ar. If participant is currently symptomatic of alcohol withdrawal, Study Visit 2 will be rescheduled. In addition, at both visits participants complete breath and self-report tests as outlined above and detailed in table below. Upon completing their final study visit all participants will be debriefed and receive their final study payment.

Participants receive partial compensation at each Study Visit; they receive \$320 for study procedures (approximately 16.5 hrs across screening visit, three study visits and four medical monitoring visits), and up to \$200 in bonuses: \$25 for attending their first hospital visit, \$25 for keeping all their original appointments, \$25 for being on time to all their hospital visits, \$25 for medication compliance (at least 90%), and \$100 for attending all visits and completing all study procedures. Total compensation is therefore up to \$520 If participants are deemed not eligible at the screening session they will be paid \$25 at that time.

| Table 1: Overview of Study Procedures and Timeline CATEGORY | PROCEDURE | Screening Visit | STUDY VISIT 1 | MONITORING VISITS | STUDY VISIT 2 | STUDY VISIT 3 |
|---|--|-----------------|------------------|-------------------|-------------------|------------------|
| TREATMENT DAY: | | DAY 0 | DAY 1 | DAY 6, 10, 14, 18 | DAY 29 | DAY 57 |
| SCREENING | | | | | | |
| | Consent | Х | | | | |
| Eligibility | Inclusion/exclusion criteria - self-report | Х | | | | |
| | Inclusion/exclusion criteria - medical | | Х | | | |
| Lab chemistry | Blood chemistry (Chem-12: CBC, TSH) | | Х | | | |
| D 1.115 | In-stream pregnancy test | Х | | | | |
| Pregnancy test (females only) | Urine analysis pregnancy test | | Х | Х | Х | |
| | Medical history | | Х | | | |
| | Concomitant medications | | Х | | | |
| Medical history/exam | Physical exam | | Х | | | |
| | Vital signs | | Х | Х | | |
| | ECG | | Х | | | |
| Psychiatric evaluation | SCID | Х | | | | |
| Self report assessment battery | Self report (Qualtrics) battery | Х | Х | | | |

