| SAFETY & COMPLIANCE | | | | | | |
| Study visit monitoring | Vital signs; Adverse events | | Х | | Х | Х |
| Treatment monitoring | Monitoring visits: Adverse events; vitals | | | Х | | |
| Treatment monitoring | Staff phone calls: Adverse events | | | | Day 2, 36, 43, 50 | |
| | Phone call reminder | | | Х | Х | Х |
| Medication compliance | Pill counts; self-report | | | X | Х | Х |
| | Review of smart caps logs (opening times/dates) | | | X | Х | X |
| Behavioral intervention | Brief motivational intervention (following NPU task) | | Х | | Х | On lapse |
| Acute craving (for study release) | Desire for Alcohol Scale (following NPU task; repeat as needed) | | Х | | Х | |
| OUTCOMES | | | | | | |
| Stress reactivity | Startle potentiation and self-report negative affect in NPU task | | Х | | Х | |
| | Perceived Stress Scale | | Past w eek | Past w eek | Past w eek | Past w eek |
| Alcohol use | Blood alcohol concentration (via breath test) | Х | Х | X | Х | Х |
| | TLFB (continuous abstinence, days drinking/w eek, drinks/day) | | Since last visit | Since last visit | Since last visit | Since last visit |
| Craving | Penn Alcohol Craving Scale | | Past w eek | Past w eek | Past w eek | Past w eek |

C4. Doxazosin Dosing Schedule

| TABLE 2 | TREATMENT DAY | DISPENSATION DAY (mg/capsule) | DAILY DOSE |
|-----------|---------------|-----------------------------------|------------|
| TREATMENT | 1 - 5 | Day 1: Study Visit 1 (1 mg) | 1 mg qd |
| | 6 - 9 | Day 6: Monitoring Visit 1 (2 mg) | 2 mg qd |
| | 10 - 13 | | 4 mg qd |
| | 14 - 17 | | 6 mg qd |
| | 18 - 28 | Day 18: Monitoring Visit 4 (4 mg) | 8 mg qd |
| | 29 - 56 | Day 29: Study Visit 2 (4 mg) | 8 mg qd |
| TAPER | 57 | Day 57: Study Visit 3 (6 x 1 mg) | 6 mg qd |
| | 58 | Day 58 (4 x 1 mg) | 4 mg qd |
| | 59 | Day 59 (2 x 1 mg) | 2 mg qd |
| | 60 | Day 60 (1 x 1 mg) | 1 mg qd |

All doxazosin and matched-placebo capsules will be prepared and blinded by the University of Iowa Pharmaceuticals, randomized by the UW Pharmaceutical Research Center and distributed through the UW CRU. Half the participants (N=80) will receive doxazosin and half (N=80) will receive a matched number of placebo pills daily for 8 weeks of

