If the participant affirms that they drove themselves, we will offer to call a cab or a friend to drive them. If this offer is declined, we will suggest that they should stay in the CRU or ARC until their BAC registers below 0.03. This release criterion has been used for many years in our other UW research that involves alcohol administration to research participants. As such, it seems equally appropriate for release for an ineligible participant who has self-administered their own alcohol. By way of comparison, a BAC of 0.08 is considered per se evidence of impairment from alcohol and with a BAC of > 0.05 alcohol impairment can be considered a contributing factor when accident or injury occurs.

If the participant declines to stay and indicates they plan to drive themselves, we will tell the participant that we will call the campus police so that the participant can make a more informed decision about what course of action to take. If the participant continues to indicate they plan to drive, we will call the campus police if the participant is driving away and provide information about the possibility of an impaired driver in the vicinity. We will not reveal the participant's name to the police in order to protect their confidentiality.

Statistical Analysis:

Planned Data Analysis for Specific Aims

Analyses for quantitative and dichotomous dependent measures will be accomplished within either General or Generalized (binomial family with logit link function) Linear Models, respectively, using R¹⁴⁰. In the sections below, we briefly describe the primary factors in statistical models to evaluate each Specific Aim. All models will include number of days abstinent at Visit 1 as an interactive between-subjects regressor to evaluate if drug effects and outcomes are comparable across alcoholics who vary in their previous duration of abstinence (1-8 weeks) on study initiation, although this has not moderated the effects on NPU task in our preliminary studies. Numerous individual difference measures (e.g., sex, mood/anxiety disorder comorbidity, tobacco use, trait affect, alcohol dependence severity, other treatment) are available to add to these models as interactive between-subject regressors in secondary analyses to evaluate possible individual difference moderators of drug effects.

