AIM 1: Unpredictable startle potentiation from the NPU task at 4 weeks will be analyzed in separate general linear models controlling for baseline NPU responses (Visit 1) with repeated measures on Condition (unpredictable vs. predictable shock). A between-subjects regressor for Treatment (8 mg doxazosin vs. placebo) will be included. Aim 1 predictions will be supported by significant Treatment X Condition interactions with doxazosin producing selectively larger reduction in startle potentiation during unpredictable relative to predictable shock.

AIM 2: Any heavy drinking (coded yes vs. no dependent if the participant reported any days where they consumed >4 drinks per day in men/ >3 drinks per day in women during the medication period) will be analyzed in a generalized linear models with a between-subjects regressor for Treatment (8 mg doxazosin vs. placebo). To be conservative, this analysis will be pursued as an intent to treat (ITT) analysis. Aim 2 predictions will be supported by significant Treatment effects with doxazosin producing selectively lower proportion of participants reporting any heavy drinking. This outcome is measured at Visits 2 & 3 and can be obtained even if the participant arrives with positive BAC.

Timeline

This project will be completed within five years of its funding. This goal is reasonable given our team's expertise in conducting both randomized controlled trials and psychophysiological laboratory research working with drug administration, community participants, and stress reactivity. Based on prior recent experience with a similar population of alcoholics who completed multiple laboratory visits, we anticipate that 85% of participants who complete the first visit will return to complete the study. We can complete up to five study visits per week and expect to average approximately 3 study visits per week to account conservatively for no-shows, failed eligibility criteria, equipment failure, and other data loss. We anticipate completing data collection in 4 years, allowing time at the beginning of the grant period for set-up and final pilot testing and the end of the grant period for manuscript preparation.

Protection of Human Subjects

D1. Risks to the Subjects

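### Aim 2 gives no code for absent or partial drinking reports, and no drinking assessment is described after removal from the study, so ITT alone does not make the test conservative

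*Combined protocol and SAP*

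**What the plan says.** Under Statistical Analysis, AIM 2, any heavy drinking is "coded yes vs. no dependent if the participant reported any days where they consumed" more than 4 drinks (men) or more than 3 (women) in a day during the period on medication. The analysis set is justified in one sentence: "To be conservative, this analysis will be pursued as an intent to treat (ITT) analysis". On collection: "This outcome is measured at Visits 2 & 3", with the remark that a positive breath test does not prevent it. Non-attendance is not covered, and no imputation or sensitivity analysis appears.

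C3 has timeline follow-back (TLFB) at Visits 2 and 3 "to assess drinking since the previous visit to index drinks per days to asses heavy drinking days for this 8 week treatment period". Table 1 goes further: the row "TLFB (continuous abstinence, days drinking/w eek, drinks/day" is marked as covering the time since the last visit at the monitoring visits as well. C5 adds check-ins on Days 36, 43 and 50, by phone or electronic survey, that ask about alcohol use.

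Randomisation closes Visit 1 (C3: "After the NPU task, participants will be randomly assigned to drug group"). Under Timeline, "we anticipate that 85% of participants who complete the first visit will return to complete the study".

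On side effects, C5 stops titration at the highest dose tolerated, and D2 (item 5) allows a modified titration. D2 (item 5) also takes people with significant side effects out of the study, and D5 does so for severe ones. For those who withdraw, C4 describes only the taper.

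**The concern.** ITT settles who is analysed and in which arm. It does not supply an outcome for someone whose reports stop early. A heavy day already reported makes that person a 'yes' whatever happens later. The open case is the leaver with no heavy day so far. Because the outcome is coded from what was reported, the literal reading makes that person a 'no', which counts unobserved weeks as weeks without heavy drinking.

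If the removal wording is followed as written, outcome loss can depend on treatment. D1 lists the side effects of doxazosin and says that fainting and orthostatic hypotension can follow the first dose or a dose increase. The increases fall on Days 6 to 18 (Table 2). More frequent or earlier exits on doxazosin are therefore plausible, though not shown.

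Aim 2 is the only planned test of a clinical outcome. Without a rule, its result could turn on a coding choice made after the data are seen.

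**Working it through.** The plan states no alpha, power, event rate or effect size for Aim 2, so there is no figure of its own to reproduce.

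**Expected leavers.** 160 × (1 − 0.85) = 24. All 24 fall inside the ITT set if 'first visit' means Visit 1. If it means screening, some leave before randomisation and the number is smaller.

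**Inputs for the illustration.** From the documents: 80 per arm, 8 weeks (56 days). Assumed: true 8-week rate r = 50% in both arms, leavers and stayers alike; no drug effect; constant hazard; two-sided 5% test (2.5% per side); leavers without a reported heavy day coded 'no'; reports complete up to the exit day t.

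**Formula.** Share of eventual heavy drinkers and others who have had a heavy day by day t: F(t) = 1 − (1 − r)^(t/56).
- F(14) = 1 − 0.5^0.25 = 0.159
- F(28) = 1 − 0.5^0.5 = 0.293

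Observed rate with dropout d = (1 − d) × r + d × F(t).

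**Doxazosin dropout 17.5% (14 of 80), placebo 12.5% (10 of 80).**
- Doxazosin: Day 14 exit, 0.825 × 0.5 + 0.175 × 0.159 = 44.0%; Day 28 exit, 46.4%.
- Placebo: Day 28 exit, 0.875 × 0.5 + 0.125 × 0.293 = 47.4%; Day 14 exit, 45.7%.

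Exact enumeration of two binomials with a pooled z test gives:

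| Exit day, doxazosin / placebo | Observed rates | False results favouring doxazosin |
|---|---|---|
| 28 / 28 | 46.4% vs 47.4% | 3.2% |
| 14 / 14 | 44.0% vs 45.7% | 3.8% |
| 14 / 28 | 44.0% vs 47.4% | 6.0% |
| 28 / 14 | 46.4% vs 45.7% | 1.9% |

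With 15% dropout in both arms and equal exit days the rate is 2.4%, so there is no bias. For the 14 / 28 row, true rates of 30% to 60% give 4.9% to 7.0%. With a wider split, 20% / 10%, the results are 4.3% (28 / 28), 8.3% (14 / 28) and 2.9% (28 / 14).

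**Planned model.** The section states: "All models will include number of days abstinent at Visit 1 as an interactive between-subjects regressor". Centring is not stated. Simulation of that logistic model (20,000 trials, days abstinent uniform on 7 to 56 and unrelated to outcome) moves the 6.0% to about 6.4% if days are centred and about 3.6% if not.

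**Opposite direction.** Take 15% dropout in both arms, nothing captured from leavers, and an overall true rate of 50% in both. Suppose 50% of doxazosin leavers but a share q of placebo leavers drank heavily. Observed rates are 0.50 − 0.15 × 0.50 = 42.5% and 0.50 − 0.15 × q. For q = 60%, 75% or 100%, placebo shows 41.0%, 38.75% or 35.0%, and false results favouring placebo are 3.6%, 6.6% or 15.7%.

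**What imputation can do.** In the q = 100% case the placebo completers' rate is (0.50 − 0.15)/0.85 = 41.2%, against 50.0% on doxazosin. Imputing by arm reproduces that 8.8-point gap, no better than the 7.5 points from coding 'no'. Only recovered follow-up removes it.

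**The case against.** The strongest reply is that the follow-up half rests on silence. The removal wording sits in safety sections. The declared ITT analysis, and the care taken to obtain the outcome despite a positive breath test, suggest an intent to keep outcomes. That stands as far as it goes: the documents do not forbid later assessment, and a reader who infers that they do goes too far. They also do not provide for it.

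Second, nothing ties the 24 expected leavers to side effects. The 85% comes from earlier laboratory-visit experience, C5 expects good tolerance, D5 calls severe side effects unlikely, and completion bonuses and motivational sessions support retention. This also stands. Side effects are a route by which loss could depend on treatment, not a finding that it will.

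Third, 6.0% needs two imbalances at once, more exits and earlier exits on doxazosin. With both arms leaving at Day 28, total two-sided error is 3.2% + 1.7% = 4.9%, not inflated overall, and reversed exit days give 1.9%. Errors favouring placebo cannot produce a false claim of benefit, although they can mislead about the drug.

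These points limit the size of the problem. They do not supply the missing rule.

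**Conclusion.** The concern holds as a gap in the outcome rule and in the description of follow-up. The label 'conservative' is not earned by ITT alone: the direction of any error depends on which arm loses more or earlier follow-up and on drinking after exit, and there is none if all three are equal by arm.

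A reader might infer that the Aim 2 test is biased towards doxazosin, or that leavers will be coded 'no'. The documents support neither. The 'no' is the literal reading of the coding sentence, not a stated intention, and the documents give no dropout by arm, exit days or event rate. The 1.9% to 6.0% range is an illustration under the listed assumptions. Confidence is medium. The point should be fixed because the choice can affect the only clinical-outcome test.

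**What to change.** 1. Without changing when medication is stopped, separate stopping study medication from leaving the study in C4, D2 (item 5) and D5. Continue TLFB through Day 57, by phone if needed, for every randomised participant who has not withdrawn consent. If this is already intended, say so.
2. In AIM 2, define the outcome window as the fixed 8 weeks after randomisation (Days 1 to 56), whether or not medication continues. Tied to the period on medication, the window could be read as ending when a participant stops, which brings back the default 'no'. Use all TLFB records, including the monitoring visits. Code 'yes' for any reported heavy day, 'no' only if the whole window is covered with none, and otherwise missing.
3. Pre-specify one method for the outcomes still missing, for example multiple imputation by arm, with missing = 'yes' and missing = 'no' as sensitivity bounds.

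The cost is a modest number of extra calls for about 24 expected leavers, through contact methods that C5 already uses, and some added analysis. Item 1 carries most of the benefit, since imputation alone does not remove relapse-driven bias. Missing = 'yes' is better kept as a bound than made the primary rule. For an assumed true 50% vs 28.5%, with 15% dropout in each arm, it moves the rates to 57.5% (0.85 × 0.50 + 0.15) and 39.2% (0.85 × 0.285 + 0.15), and power falls from 80% to 64%.

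Separately, C5, D2 (item 5) and D5 should be reconciled on which side effects lead to modified titration and which to removal. They may describe graded severity. No clinical rule is proposed here.

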At the screening visit, which will take place at the Addiction Research Center offices, general laboratory procedures and risks and benefits will be explained to the participants and informed consent will be obtained. Inclusion/exclusion criteria will be confirmed using interviews conducted by a bachelors- or master-level clinical psychologist (under direct supervision of a licensed clinical psychologist), a urine pregnancy test (females only), blood pressure and heart rate, and self-report questionnaires (Medical Screening Questionnaire) (see Appendix C). Participants will complete the CIWA-Ar; if the participant is currently symptomatic of alcohol withdrawal, Study Visit 1 will be scheduled at least one week in the future. The psychologist will confirm alcohol use disorder diagnosis, establish that the potential participant is free from severe and persistent mental illness and current suicidal ideation, and document any other current Axis I disorders by administering the Structured Clinical Interview for DSM Disorders-Research Version (SCID-RV; see letter of support from [name]). The SCID-RV interviews will be audio recorded to permit clinical supervision and inter-rater reliability. These recordings will be deleted immediately after review.

At Study Visit 1 (CRU), participants will provide a breath sample to verify an initial blood alcohol concentration (BAC) of 0.00 (Alcosensor IV; Intoximeters, Inc.). Participants will complete the CIWA-Ar; if they are currently symptomatic of alcohol withdrawal, Study Visit 1 will be rescheduled at least one week in the future. The provider will conduct a medical history/exam and review current medication. Medical staff will collect orthostatic vital signs, a blood sample for lab tests, and a urine sample to verify no pregnancy (females only). The provider will also conduct an ECG (see further details about safety procedures in Protection of Human Subjects section). Participants will then complete a variety of self-report batteries, for post hoc individual differences analyses (see Appendix A).

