Appendix A: Surveys, Questionnaires and Interviews

All self-report surveys, questionnaires, and interviews are completed by the participant in the privacy of the Addiction Research Center or an outpatient room in the Clinical Research Unit in the University of Wisconsin Hospitals and Clinics. Questionnaires are administered on paper, lab computers, or iPads via the UW-Madison Qualtrics Survey Hosting Service.

Surveys and Questionnaires

- Alcohol Dependence Scale (ADS): Standard questionnaire providing a quantitative measures of the severity of alcohol dependence.
- Alcohol Use Disorders Identification Test (AUDIT): Standard questionnaire about quantitative alcohol
 use.
- Alcohol Use History Questionnaire questions about alcohol use history
- Anxiety Sensitivity Index (ASI-3): Standard questionnaire about anxiety.
- Demographics: Standard questionnaire about age, gender, race, and ethnicity.
- Depression Anxiety Stress Scales (DASS): Standard questionnaire about depression and anxiety symptoms.
- Desires for Alcohol Scale (DAQ): Subset of items from standard questionnaire about the participants' desire/craving of alcohol.
- Distress Tolerance Questionnaire (DTQ): Standard questionnaire about reactions to stressful situations.
- Feedback: Standard questionnaire about the participant's experience in the study.
- Intolerance of Uncertainty Scale (IUS): Standard questionnaire about anxiety and reactions to uncertainty.
- Mindful Attention Awareness Scale (MAAS): Questions about positive/negative affect and mindfulness
- Multidimensional Personality Questionnaire- Short form (MPS): Standard questionnaire about personality and temperament.
- Obsessive Compulsive Drinking Scale (OCDS): Standard questionnaire about obsessionality and compulsivity related to craving and drinking behavior.
- Penn Alcohol Craving Scale (PACS): Standard questionnaire for assessing alcohol craving.
- Perceived Stress Scale (PSS): Standard guestionnaire about the perception of stress.
- Post-Experiment Questionnaire (PEQ): Standard questionnaire about the participants' emotions during the experiment.

Interviews

- Clinical Institute Withdrawal Assessment of Alcohol Scale, Revised (CIWA-Ar): Standard assessment of Alcohol Withdrawal Symptoms.
- Screening Survey (previously referred to as MSQ): Standard questionnaire from our laboratory about health-related behaviors for screening purposes.

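### The primary Aim 2 model leaves out baseline severity, craving and sex, although all are collected; prespecifying them would be a cheap gain in power and in protection against chance imbalance

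*Combined protocol and SAP*

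**What the plan says.** Under Planned Data Analysis for Specific Aims, the AIM 2 paragraph states that the yes/no outcome "will be analyzed in a generalized linear models with a between-subjects regressor for Treatment (8 mg doxazosin vs. placebo"), by intention to treat. The opening of that section sets the binomial family with logit link and adds one covariate throughout: "All models will include number of days abstinent at Visit 1 as an interactive between-subjects regressor".

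Other baseline measures are optional. The section lists "sex, mood/anxiety disorder comorbidity, tobacco use, trait affect, alcohol dependence severity, other treatment) are available to add to these models", and confines them to moderator use: "alcohol dependence severity, other treatment) are available to add to these models as interactive between-subject regressors in secondary analyses". Craving is not named in any model.

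The data are there. Appendix A lists the "Alcohol Dependence Scale (ADS): Standard questionnaire providing a quantitative measures of the severity of alcohol dependence". Section C3 places the questionnaires at Visit 1, ahead of the NPU task: "Participants will then complete a variety of self-report batteries, for post hoc individual differences analyses". Table 1 shows the self-report battery at screening and Visit 1 only, and PACS (past week) from Visit 1. Section C7 adds that craving is measured on arrival. Randomisation follows the NPU task at Visit 1 and is stratified by sex alone (section C3). The first dose is taken at home that evening.

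**The concern.** Severity of dependence and craving before treatment are plausible predictors of heavy drinking over the next eight weeks. Neither is balanced by design and neither is in the primary Aim 2 model. The Aim 1 model, by contrast, controls for the baseline value of its own outcome.

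Two things are at stake. The first is power: the endpoint is binary, the sample is 160, and the documents give no power calculation for it. The second is how the result reads if the arms happen to differ on severity or craving. The open list of measures that may be added later means that an adjustment chosen after seeing such an imbalance could be challenged as selective. A covariate set named in advance avoids that.

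**Working it through.** **Inputs from the documents.** 80 per arm (section C4); logistic model with Treatment and days abstinent as an interactive term (Planned Data Analysis). The documents state no alpha, power, event rate or effect size for Aim 2, so there is no planned figure to reproduce.

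**Assumptions.** Two-sided 0.05; a 20-point reduction from placebo rates of 40%, 50% or 60%; one standardised baseline covariate whose odds ratio per SD (OR/SD) is varied from 1.0 to 2.5, because the documents do not give its strength.

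**Step 1: scale without covariates.** With n = 80 and p̄ the mean of the two rates,

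power = Φ{[0.20 − 1.96·√(2p̄(1−p̄)/n)] / √([p₀(1−p₀)+p₁(1−p₁)]/n)}.

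For 50% vs 30%: (0.20 − 1.96×0.0775)/0.0758 = 0.635, so power is 74%. The same formula gives 79% for 40% vs 20% and 72% for 60% vs 40%.

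**Step 2: power with and without the covariate.** I used 4,000 simulated trials per setting. Both models contain Treatment, days abstinent (centred) and their interaction; the second adds the covariate as a main effect.

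| Rates | OR/SD | Planned model | With covariate | Gain (points) |
|---|---|---|---|---|
| 50% vs 30% | 1.0 | 74.1% | 74.0% | −0.1 |
| 50% vs 30% | 1.3 | 74.6% | 75.4% | 0.8 |
| 50% vs 30% | 1.5 | 74.4% | 75.5% | 1.1 |
| 40% vs 20% | 1.5 | 78.6% | 80.5% | 1.9 |
| 60% vs 40% | 1.5 | 71.6% | 73.5% | 1.9 |
| 50% vs 30% | 2.0 | 74.1% | 78.2% | 4.1 |
| 40% vs 20% | 2.0 | 78.9% | 82.2% | 3.3 |
| 60% vs 40% | 2.0 | 70.4% | 75.2% | 4.8 |
| 50% vs 30% | 2.5 | 73.2% | 79.8% | 6.6 |

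The Monte Carlo standard error of one power figure is √(0.74×0.26/4000) = 0.7 points, so the smallest gains are not sharply resolved.

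**Step 3: where the gain lies.** At 50% vs 30% and OR/SD 2.0, the standard error of the log odds ratio rises with adjustment, from 0.339 to 0.362. The sampling SD of the standardised risk difference falls from 7.61 to 7.29 points, a relative efficiency of 1.09, worth about 0.09×160 ≈ 15 participants. At OR/SD 2.5 it is 1.15, worth about 25 when computed from the unrounded 1.153.

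**Step 4: chance imbalance.** The between-arm difference in a standardised covariate has SD √(2/80) = 0.158. The probability that it exceeds 0.3 SD in either direction is 2[1−Φ(0.3/0.158)] = 5.8%. With no drug effect (50% in both arms), the slope of the planned-model risk difference on imbalance, multiplied by 0.3, gives the shift:

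| OR/SD | Slope | Shift at 0.3 SD (points) |
|---|---|---|
| 1.5 | 0.107 | 3.2 |
| 2.0 | 0.146 | 4.4 |
| 2.5 | 0.196 | 5.9 |

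For comparison, the sampling SD of the risk difference is about 8 points in that setting. With the covariate in the model the slope is at most 0.011 in absolute value in these rows, a shift of about 0.3 points.

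**Step 5: validity.** With no drug effect, the rejection rate was 4.5-5.8% under the planned model and 5.0-5.8% with the covariate.

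**The case against.** The strongest reply is that nothing here is wrong. Randomisation makes the planned test valid, Step 5 confirms it, and chance imbalance is already part of the standard error. That stands: omitting these covariates neither biases the test over repeated randomisation nor inflates type I error.

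The second reply is that the benefit rests on an unknown. No section says how strongly ADS or PACS predicts heavy drinking, and eligibility (at least moderate disorder, one to eight weeks abstinent, pursuing abstinence) may narrow their spread. That also stands. A reader might call these the main prognostic factors; the documents support only that they are plausible ones, and the gain could be nil.

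Third, the plan is not a treatment-only analysis, as the AIM 2 paragraph read alone might suggest. Days abstinent, already in every model, is itself a drinking-history covariate, and severity is listed for secondary use. This is correct, but secondary moderator terms do not help the primary test.

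Fourth, a reader might say that precision is given away. On the log odds scale the opposite holds: adjustment raises the standard error (Step 3). The benefit is in power and in the standardised risk difference.

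Finally, a reader might infer that the timeline follow-back (TLFB) interview cannot supply a baseline, since Table 1 has it at Visit 1 covering only the interval since the previous visit. Appendix A describes it as covering the past month. That window could reach drinking before abstinence in participants with short abstinence. The documents disagree, so the inference is not supported.

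**Conclusion.** The point holds as a recommended improvement, not as an error. The primary Aim 2 model omits baseline severity, craving and the stratification factor, although all are available before the first dose.

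Under the stated assumptions the power gain runs from nil to about 7 points, and reaches about 4 only if the covariate has an odds ratio near 2.0 per SD. The 3-to-6-point shift from a 0.3 SD imbalance applies for OR/SD 1.5-2.5, can favour either arm, and is smaller for weaker predictors. An unrelated covariate cost essentially nothing in the simulation.

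The figures are for one added covariate. The gain from ADS and PACS together depends on their joint strength, which the documents do not give.

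**What to change.** In the AIM 2 paragraph, fix the model before unblinding as Treatment, days abstinent (as already planned), sex, ADS total and Visit 1 PACS, the last three as main effects. If PACS is not taken before randomisation at Visit 1, which the documents leave open, use craving on arrival instead. State a simple rule for missing baseline scores, such as mean imputation with a missing indicator, so that no randomised participant drops out of the intention-to-treat analysis. Report the standardised risk difference beside the odds ratio.

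Separately, reconcile the TLFB look-back window between Table 1 and Appendix A.

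The cost is analysis-plan wording and a few extra model terms; no new data or visits are needed. The odds ratio becomes conditional on the covariates, which is why the standardised risk difference should accompany it.
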